#### **CONFIDENTIAL INFORMATION**

The information in this study protocol is confidential. Any disclosure, copying or distribution of the information contained within is strictly prohibited without written consent from University of Florida.

Abnormal laboratory test results and positive pregnancy test results will be flagged by the laboratory. All clinically important abnormal laboratory tests occurring during the study will be followed until they resolve (return to normal or baseline values) or stabilize, or until they are considered by the Investigator to be no longer clinically significant.

COVID-19 nasal collection and testing may take place at this visit if travel time allows for the participant - Due to COVID-19 Pandemic, nasal collection and testing of the participants has been implemented to determine if the participant is COVID negative. The collection is done at UF Springhill collection site and testing is completed at Rocky Point Labs overnight with results placed in EPIC. The results of the testing will be provided to the participant once results are posted in EPIC. This collection and testing will continue throughout participation in the study.

#### **12.3.8. Lumbar Puncture Analysis:**

CSF fluid will be drawn from the patient for the following disease evaluations:

*Inflammation and RAN protein levels:* Neuroinflammation markers and/or C9 RAN proteins present in CSF will be analyzed using a highly sensitive MesoScale Discovery (MSD) electrochemiluminescence assays and other assays. For some of these studies custom antibodies generated and characterized by the PI will be used. The RAN MSD assays have been optimized for the detection of the C9 GP RAN proteins. These and other molecular studies will be done in the [name]. Any remaining CSF will be stored indefinitely in the Center for NeuroGenetics bank for future studies.

Due to the COVID-19 Pandemic, and only for the participants currently enrolled (3) in this study, this procedure may be completed in the participant's home area and the samples shipped to the [name] Lab for analysis. The lumbar puncture will be completed by a licensed physician who is qualified to perform this procedure and agrees to complete the procedure per the protocol.

*Metabolomics:* The level of Metformin in the CSF and levels of various metabolomics components will be analyzed by traditional liquid chromatography tandem mass spectrometry of (UPLC/MS/MS) in the [name] lab.

#### **12.3.9. Speech and Swallowing Function:**

The following will be performed at the Fixel Institute for Neurological Diseases, in room 1010.6 as directed by [name], a Certified Speech Language Pathologist. The following procedures and outcomes will be performed and derived:

---

#### **CONFIDENTIAL INFORMATION**

The information in this study protocol is confidential. Any disclosure, copying or distribution of the information contained within is strictly prohibited without written consent from University of Florida.

- **Videofluoroscopic Swallow Study (VFSS):** VFSS will be performed using a Phillips BV Endura fluoroscopic C-arm unit (GE OEC 8800 Digital Mobile C-Arm system type 718074) that is housed at Fixel and used for clinical and research purposes. Fluoroscopic data will be captured in high resolution at 30 frames per second and in the lateral field of view using a TIMS Dicom (Version 3.2, TIMS Medical, TM, Chelmsford, MA). Patients will be seated and will complete a standardized bolus protocol consisting of: 1) three 5ml thin liquid barium; 2) a regular sip of thin liquid taken from a cup containing 90cc of thin liquid; 3) consecutive cup sip of remaining barium; 4) three teaspoons of thin honey consistency barium; 5) two teaspoons of pudding-thick barium; 6) graham cracker with pudding-thick barium; and a 7) 13mm barium tablet (EZ-Disk). To ensure patient safety, a bail out criterion will be utilized and the VFSS will cease on the third episode of frank aspiration or residue greater than 75% of either vallecular or pyriform housing that is unable to be cleared with strategies. Once the study is completed, recordings will be saved and digitally backed up for subsequent analyses.
- **VFSS Outcomes:** Two independent, blinded and trained raters will perform analyses on the data for every bolus using validated procedures. Discrepancies between raters will be flagged and resolved at a consensus meeting and three swallows from each evaluation will be repeat rated at random for evaluation of intra-rater reliability. VFSS measures are summarized below and include indices of Global Swallowing Function (Appendix E) and Swallowing Safety (Appendix F).
- **Global Swallowing Function:** The validated Dynamic Imaging Grade of Swallowing Toxicity (DIGEST) will be performed on all collected videofluoroscopic swallowing studies to assess global swallowing function (Hutcheson and Fuller, 2015). The DIGEST total score is determined using the composite of individual airway safety and bolus efficiency subscores (range: 0-4). The DIGEST total is rated on a 5-point ordinal score ranging from 0 (no dysphagia) to 4 (life-threatening dysphagia). For statistical analysis, DIGEST total scores will be compared within individuals between the Visit 1 (baseline), Visit 3 (12 weeks) and Visit 4 (24 weeks). DIGEST total scores of <2 indicate functional swallowing and scores  $\geq 2$  indicate dysphagia. The DIGEST scoring schema is provided in Appendix E.
- **Swallowing Safety:** The Penetration-Aspiration scale [(PAS), (Rosenbek et al., 1996)] is a validated eight-point ordinal scale indexing the degree of airway invasion during swallowing, the participant's response, and whether the invasive material is successfully ejected from the airway. PAS scores of 1 and 2 are considered safe, while scores between 3 and 5 indicate penetration of material in the upper airway at or above the level of the true vocal folds.

---

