### Outcome Measures:

**Primary:** 1. ALSFRS-R score

**Secondary:** 2. Soluble GP in blood; 3. Swallowing physiology (PAS, DIGEST); 4. PFT's (FVC, PCF); 5. MRI/DTI outcomes.

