**CONFIDENTIAL INFORMATION**

The information in this study protocol is confidential. Any disclosure, copying or distribution of the information contained within is strictly prohibited without written consent from University of Florida.

PAS scores greater than 6 indicate aspiration of material below the level of the true vocal folds into the airway. For statistical comparisons across airway safety status levels the convention is as follow: safe swallowing = PAS  $\leq 2$  and unsafe swallowing = PAS  $\geq 3$ .

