## APPENDIX F

### Penetration-Aspiration Scale (PAS)

Score	Description of Events
1	Material does not enter airway.
2	Material enters the airway, remains above the vocal folds.
3	Material enters the airway, remains above the vocal folds, and is not ejected from the airway.
4	Material enters the airway, contacts the vocal folds, and is ejected from the airway.
5	Material enters the airway, contacts the vocal folds, and is not ejected from the airway.
6	Material enters the airway, passes below the vocal folds, and is ejected into the larynx or out of the airway.
7	Material enters the airway, passes below the vocal folds, and is not ejected from the trachea despite effort.
8	Material enters the airway, passes below the vocal folds, and no effort is made to eject.

---

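### Cutting PAS to safe/unsafe for the statistical comparisons hides all worsening within the unsafe class and gives up much of the sensitivity available from 16 subjects

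*Combined protocol and SAP*

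**What the plan says.** Section 12.1 (Outcome Measures) lists "Swallowing physiology (PAS, DIGEST") as one secondary outcome and does not rank the two scales.

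Section 12.3.9 describes both. PAS "is a validated eight-point ordinal scale indexing the degree of airway invasion during swallowing". The section then sets a rule for its analysis: "For statistical comparisons across airway safety status levels the convention is as follow", namely safe at PAS 2 or below and unsafe at 3 or above. It names no visit pair and no test for PAS. For DIGEST, it says that "DIGEST total scores will be compared within individuals between the Visit 1 (baseline), Visit 3 (12 weeks) and Visit 4 (24 weeks"), and that "The DIGEST total is rated on a 5-point ordinal score ranging from 0 (no dysphagia) to 4 (life-threatening dysphagia"). A cut at 2 is also given for DIGEST, as a guide to interpretation.

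Appendix F defines the PAS levels. Score 3 is material that stays above the vocal folds and is not ejected. Score 8 reads "Material enters the airway, passes below the vocal folds, and no effort is made to eject".

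Section 15.3 names swallowing only as an impact to be assessed. Section 15.7 promises summary statistics, excludes formal tests on tolerability and safety endpoints (its list of visits stops at Visit 3), excludes efficacy analysis, and leaves room for additional tests if needed.

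**The concern.** The PAS cut is a stated analysis rule, so it can be judged as one. It puts six of the eight levels into a single class, and those six run from material left above the vocal folds to silent entry below them. A within-subject comparison on that cut registers only a crossing between 2 and 3.

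Two features of the trial make this matter. First, eligibility rests on FOIS (4 or above) and sets no limit on PAS, so subjects may enter already unsafe; on the cut they can only stay the same or improve. Second, safety is the primary objective, ALS is progressive, and worsening is the direction of interest. Section 12.3.9 plans to rate every bolus, so the finer score will exist. The cut discards it only at the point of comparison.

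**Working it through.** **Inputs from the documents.** PAS levels 1–8 and their definitions (Appendix F); cut at 2/3 (Section 12.3.9); VFSS at Visits 1, 3 and 4 (Table 3); about 16 subjects (Section 15.4, a recruitment figure with no power inputs). The plan gives no alpha, effect size or category frequencies for swallowing, so it has no figure of its own to reproduce.

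**Step 1: which worsening moves the cut can show.** A worsening move is any pair of levels (a, b) with b > a.
- All moves: 8 × 7 / 2 = 28.
- Crossing the cut (from 1 or 2 to one of 3–8): 2 × 6 = 12.
- Within the unsafe class (levels 3–8): 6 × 5 / 2 = 15.
- Within the safe class (1 to 2): 1.
- Hidden by the cut: 15 + 1 = 16 of 28, or 57%.

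This counts what the scale can express. It does not say how often patients make each move.

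**Step 2: how many crossings a paired test on the cut needs.** With m subjects crossing, all in one direction, the exact two-sided McNemar p-value is 2 × 0.5^m.
- m = 5: 2 / 32 = 0.0625.
- m = 6: 2 / 64 = 0.031.

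So at least 6 of 16 subjects must cross upward with none crossing back. If one crosses back, 7 against 1 gives 2 × (1 + 8) / 256 = 0.070, and 8 against 1 gives 2 × (1 + 9) / 512 = 0.039.

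**Step 3: sensitivity under assumed inputs.** All of the following are assumptions: two-sided 0.05; 16 subjects with complete data; normally distributed latent severity; linear drift reaching 0.5 SD at Week 24; visit-to-visit correlation 0.5 to 0.85; PAS levels cut at baseline quantiles 0.40, 0.60, 0.70, 0.76, 0.82, 0.88 and 0.93. Under these shares 40% are unsafe at baseline, or 16 × 0.40 = 6.4 subjects on average. That leaves about 9.6 who could cross upward, of whom at least 6 must do so.

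Share of simulated trials in which the Visit 1 to Visit 4 comparison gives p < 0.05:

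| PAS analysis | Detected |
|---|---|
| Safe/unsafe cut, exact McNemar | about 9–11% |
| Eight-point score, exact signed-rank | about 36–71% |

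The ranges span the assumed correlations. In the same simulations the proportion unsafe rose from Visit 1 to Visit 4 in roughly 90% of trials.

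**The case against.** The strongest case against is that little rests on this comparison. Swallowing is secondary, Section 15.7 plans summary statistics and no efficacy analysis, and no decision or error rate is tied to PAS. The wording in 12.3.9 is a convention for comparing airway-safety classes; it does not say that PAS will be analysed in no other way. The eight-point data are kept, and "The DIGEST total score is determined using the composite of individual airway safety and bolus efficiency subscores (range: 0-4"), so DIGEST may pick up some worsening inside the unsafe class. With no control arm, a clearer worsening still could not be attributed to metformin.

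Most of this stands, and it limits the weight of the point. It does not remove it: the cut is the only PAS rule given for statistical comparison, and 12.3.9 and 15.7 disagree on whether such comparisons take place. Whether DIGEST compensates cannot be checked, because its scoring appendix is not in the text reviewed.

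Three stronger readings are tempting, and none is supported.
- **A reader might infer that the binary PAS will usually show no change.** It will not. Under the assumptions above, the unsafe proportion rises in roughly 90% of trials. A non-significant test is not an unchanged table.
- **A reader might infer that three DIGEST visit pairs with no deciding one inflate the false-positive rate.** Independence at 0.05 would give 1 − 0.95³ = 14.3%, but the pairs share visits and the scale is coarse. With exact signed-rank tests, the chance that any of the three is significant is about 4–9%, and the plan sets no error rate to break.
- **A reader might infer that Week 12 and Week 24 could give opposite conclusions.** They can differ on significance, which is expected if change accumulates. Significant DIGEST results in opposite directions occurred in 0 of 1,000 simulated trials in every setting tried.

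**Conclusion.** The concern holds for the PAS cut. That the cut hides 16 of 28 worsening moves, 15 of them within the unsafe class, follows from the scale and the stated cut alone. That it lowers detection of a moderate worsening to about 9–11%, from about 36–71% on the full score, depends on an assumed alpha, drift, correlations and category shares. The direction was the same at every correlation tried; the exact percentages should not be relied on.

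The absence of a named deciding contrast for DIGEST is mainly missing detail for a secondary outcome in a descriptive study. It is worth settling in the same edit. The point is modest: it should be changed because a better use of the same ratings is available at almost no cost, and it does not put the trial's primary objective in doubt.

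**What to change.** In Section 12.3.9:
- Name the within-subject change in the ordinal DIGEST total from Visit 1 to Visit 4 as the main swallowing summary.
- Beside it, report the Visit 1 to Visit 4 change in each subject's worst PAS per VFSS on the eight-point scale, as a shift table with a signed-rank estimate and 95% CI. Naming the worst score also fills a gap: every bolus is rated, but no rule reduces the ratings to one PAS value per visit.
- Keep the safe/unsafe proportions and all Visit 3 comparisons, labelled descriptive.

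In Sections 12.3.9 and 15.7, reconcile the planned statistical comparisons with the statements that no formal tests on safety endpoints and no efficacy analysis will be done. If description only is intended, the shift table and the estimate with its interval still serve, without a p-value.

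The cost is a few sentences and no new data, since both scales come from the VFSS already scheduled at Visits 1, 3 and 4. An ordinal change is harder to read clinically than a safe/unsafe percentage, which is why that table stays. Without a control arm, neither summary can separate a drug effect from disease progression, and the report should say so.

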**CONFIDENTIAL INFORMATION**

The information in this study protocol is confidential. Any disclosure, copying or distribution of the information contained within is strictly prohibited without written consent from University of Florida.

PAS scores greater than 6 indicate aspiration of material below the level of the true vocal folds into the airway. For statistical comparisons across airway safety status levels the convention is as follow: safe swallowing = PAS  $\leq 2$  and unsafe swallowing = PAS  $\geq 3$ .

#### 12.3.9.1 Pulmonary Function

The following will be performed by trained clinical research coordinators at the Fixel Institute for Neurological Diseases:

- **Voluntary Peak Cough Flow Testing:** Participants will be seated with a nose clip in place and instructed to take a deep breath in and “cough hard like you have something stuck in your throat”. To reduce the potential for labial air leakage due to reduced orofacial muscle tone, a rubber flanged mouthpiece (MTH6400), will be attached to the end of a Mini-Wright CE0120 analogue peak flow meter device. The patient will perform three trials inter-spaced with a one-minute rest break. Outcomes will include peak expiratory flow (L/min) (PEF). The highest obtained values will be used.
- **Pulmonary Function Testing:** Forced vital capacity (% predicted) will be assessed using a hand-held digital spirometer (MD Spiro Micro 1 Spirometer).

#### 12.3.10. Imaging

The following will be performed on the Siemens or Phillips 3T system at the University of Florida under the direction of [name]:

- **Measurement of brain structure and brain function:** This experiment will require the participant to lie down on a platform that will move into an enclosed magnetic resonance imaging system for both functional magnetic resonance imaging (fMRI) and structural imaging (diffusion, T1 and T2 weighted). fMRI is a technique used to non-invasively measure changes in brain activity in relation to performance of a specific task. T1, T2, and diffusion imaging examine the macrostructure and microstructure of the brain tissue non-invasively. In brain structure measures, the participant will lie still in the MRI without performing a task. In brain function measures, the participant will perform a motor task. The participant will be asked to practice the experimental tasks described below until they feel comfortable performing them. During this task the participant will use a small pinch grip device that they will hold between the thumb and index finger. Once inside the scanner, the participant will be asked to lie still while the study staff perform a scan to provide an anatomical picture of the brain. The participant will be asked to

---

#### CONFIDENTIAL INFORMATION

The information in this study protocol is confidential. Any disclosure, copying or distribution of the information contained within is strictly prohibited without written consent from University of Florida.

complete a series of tasks during which study staff will obtain pictures of the functional changes in brain activity. During this task the participant will move their hand under different conditions. In one condition the participant will be asked to perform the task with no sensory information about the task. Study staff will refer to this task as a “self-initiated” task. No stimulus will be presented in this condition. In another condition the participant will be asked to respond to a stimulus, which will give them information regarding the timing of their movement or the extent to which they should contract their muscles. Study staff will refer to this task as an “auditory cued task” or a “visually cued task”. The participants’ goal during all movement conditions will be to move as quickly as possible.

#### **12.3.11. BDI-Fast Screen**

The BDI-Fast Screen, which assesses depression (**Appendix D**), will be administered at Visit 2, Visit 3, Phone call at 18 weeks, Visit 4, and Phone call at week 36. Subject indicating depression will be counseled by a physician prior to leaving the clinic if they are at UF and may be referred to a mental health professional.

#### **12.3.12. Subject Adherence Assessments**

Adherence to study requirements and compliance with medication will be assessed at the study visit through direct questioning by staff personnel.

### **13. SAFETY AND ADVERSE EVENTS**

The AE definitions and reporting procedures provided in this protocol comply with all applicable International Conference on Harmonization (ICH) guidelines. Study staff will carefully monitor each subject throughout the study for possible AEs. All AEs will be documented on CRFs designed specifically for this purpose. It is also important to report all AEs, especially those that result in permanent discontinuation of the investigational product being studied, whether serious or non-serious.

**Safety Review Plan and Monitoring-** Oversight of participant safety includes review of adverse events as well as study progress, data integrity and study outcomes. The study will engage a physician safety monitor to discuss issues regarding side effects and adverse events. The safety monitor is external to the clinical study and is free of any conflicts of interest to maintain independence and objectivity.

#### **Safety and study progress reviews**

---

#### **CONFIDENTIAL INFORMATION**

The information in this study protocol is confidential. Any disclosure, copying or distribution of the information contained within is strictly prohibited without written consent from University of Florida.

1. Adverse events will be reviewed by the Principal Investigator, the Co-Principal Investigator(s) and the Safety Officer
2. Study progress will be reviewed by the study investigators on a quarterly basis (e.g. Recruitment, retention, protocol adherence).
3. For each Continuing Review period, a report will include
  - a. list and summary of adverse events
  - b. whether adverse events rates are consistent with pre-study assumptions
  - c. Summary of recruitment and retention and reason for withdrawals
  - d. whether the study is on track to be completed and accomplish the stated aims.

### **13.1. Adverse Event Reporting and Follow Up**

Subjects will be instructed to inform clinic personnel of any untoward medical symptoms and/or events that may arise during the course of the study. If an adverse event is experienced by a subject, then the subject will be questioned concerning symptoms that may have occurred after the administration of the study drug. The incidence, severity and duration of all AEs will be recorded according to the following scale:

Mild	Adverse event resulting in discomfort, but not sufficient to cause interference in normal daily activities
Moderate	Adverse event resulting in discomfort that is sufficient to cause interference in daily activities.
Severe	Adverse event resulting in discomfort causing an inability to carry out normal daily activities

Subjects who withdraw due to an adverse event will be followed whenever possible until resolution of the adverse event. It may be appropriate for the subject to return to the site 2 weeks after the subject is off study to evaluate for resolution of any adverse events and to receive further information about options for future clinical care. The Investigator will decide the course of action.

---

### **13.2. Assessing Relationship to Study Drug**

The Principal Investigator/Sub Investigators will assess the relationship of all adverse reactions to the drug, using the following scale:

Probable	A clinical event, including laboratory test abnormality, with a reasonable time sequence to drug administration, unlikely to be attributed to concurrent disease or other drugs or chemicals, and which follows a clinically reasonable response on withdrawal.
Possible	A clinical event, including laboratory test abnormality, with a reasonable time sequence to drug administration, but which could also be explained by concurrent disease or other drugs or chemicals. Information on drug withdrawal may be lacking or unclear.
Unlikely	A clinical event, including laboratory test abnormality, with a temporal relationship to drug administration which makes a causal relationship improbable, and which other drugs, chemicals or underlying disease provide plausible explanation.
Unrelated	This category is applicable to AEs which are judged to be clearly and incontrovertibly due to extraneous causes (diseases, environment, etc.) and do not meet the criteria for drug relationship listed for the above-mentioned conditions.

Subjects who withdraw due to an adverse event will be followed whenever possible until resolution of the adverse event. It may be appropriate for the subject to return to the site 2 weeks after the subject is off study to evaluate for resolution of any adverse events and to receive further information about options for future clinical care. The Investigator will decide the course of action.

